9.2.3 Suspected Unexpected Serious Adverse Reaction Definition

In order to be qualified as a suspected unexpected serious adverse reaction (SUSAR), the AE must meet 3 criteria: the event is serious, there is a certain degree of probability that the event is a reaction to the study drug being researched and the nature and severity of the reaction are not in agreement with the product information (i.e., the reaction is unexpected as per the reference safety information). All SUSARs will be reported as required to the Competent Authorities and to the Ethics Committee (EC)/Institutional Review Boards (IRBs) of the countries and centers concerned.

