2.5 Measures to Minimize Bias

To facilitate interpretation of clinical data, inclusion of randomized, concurrent parallel control groups is recommended for clinical studies whenever possible. Masking of participating subjects, treating physicians and study staff is of particular importance when subject effort or perception

could bias evaluation of study endpoints, such as for measurement of visual acuity ([Glassman 2012](#)).

IVT injection is a well-established route of administration within ophthalmic indications that permits targeting of the therapeutic agent to the eye, while minimizing systemic absorption. IVT injection is used in several products for the chronic treatment of ophthalmic diseases (e.g., Lucentis®, Eylea™, Macugen®) and the risk of complications is low when injections are performed by trained ophthalmologists ([AAO 2015, Avery 2014](#)).

However, potentially severe complications to IVT injections exist, including endophthalmitis, intraocular inflammation, cataract, retinal detachment, and vitreous hemorrhage. Although the risk of severe complications is small, it is well documented ([Jager 2004](#)). Therefore, while IVT injection of the vehicle alone is theoretically feasible as a placebo control, it is not considered ethical since the physical properties of such an injection do not have potential therapeutic benefit. Hence, placebo injections will not be administered in this study to preserve subject safety.

Other possibilities than placebo injections to effect masking include alternative dosing regimens, alternative dose levels, and existing products approved for the indication being sought. There are no existing approved products for the indication under investigation.

Use of sham-procedures (i.e., no penetration of the globe) to mask subjects to treatment assignment in studies of products administered via IVT injections eliminates the risk of complications due to injection in the control arm. The sham-procedure, which closely mimics the injection procedure used for product delivery can effectively mask participants to treatment assignment; however, the masking effect is less pronounced in the case that a single subject receives both the real and sham injections in their 2 eyes ([Glassman 2012](#)).

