9.5 AESIs and Serious Adverse Events Notification

For all AESI and SAEs, regardless of suspected causality, a completed AESI/SAE/Special Situation reporting form must be sent within 24 hours of discovery of the event immediately (without undue delay) to:

DRUG SAFETY

See Study Reference Manual

Any fatal or life-threatening (i.e., imminent risk of death) event that is attributed by the Investigator to the study drug must be immediately telephoned to:

DRUG SAFETY

Phone: See Study Reference Manual for phone number

followed by submission of written case details on an AESI/SAE/Special Situation reporting form within 24 hours.

Serious AEs occurring any time after study participation that are considered by the Investigator to be possibly related to study drug must also be reported. The following are important points to remember when completing the SAE form:

- If complete information is not available, at a minimum, subject identifier, suspect drug, study center identifier, event or outcome, and Investigator assessment of causal relationship to study drug should be provided.
- A rationale for the causality assessment of an SAE should always be included, so that a better understanding of the event can be compiled.
- Follow-up information, such as laboratory reports, discharge summaries, autopsy reports, and information concerning outcome of the event should be submitted by revising the SAE form as soon as the information becomes available. Copies of source documents, with subject identifiers redacted, should be submitted only when they are written in English. If source documents are not in English, the Investigator must summarize the source documents, providing a complete English narrative that includes a description of the events as it evolved, the results of all diagnostic procedures performed, treatments administered, and outcome of the event. A query regarding a follow-up report should be answered within 5 working days from receipt of the query.
- Appropriate diagnostic tests and therapeutic measures are to be performed as necessary and reported on the SAE form.
- All SAEs must be reported to the IRB/EC, if applicable. See the [International Council for Harmonisation \(ICH\) GCP E6 \(R2\)](#), Section 4.11.1 (ICH 2016).

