9.6 Expedited Reporting of Suspected Unexpected Serious Adverse Reactions

The Sponsor or designee will fulfil reporting obligations as defined in the Safety Management Plan (SMP). The SMP details the responsibilities, processes and timelines for expedited reporting and aggregate periodic reporting to relevant recipients (e.g. Competent Authorities, Central ECs/Central IRB, Investigators etc.) across sites within the study. The SMP ensures a systematic approach to safety monitoring and promotes early issue detection to help mitigate any safety risks in clinical trial subjects.

- The Sponsor or its designee is responsible for notifying the study centers of all expedited SAEs that occur during any clinical studies that are using the study drug. The Sponsor or its designee shall also notify Central ECs and Central IRB of SUSARs or significant risks to subjects, per country requirements. All SUSARs will be reported as required to the Competent Authorities of all involved participating countries.
- The Investigator will notify local IRB/EC of SUSARs or significant risks to subjects, per local country requirements. The Investigator must keep copies of all AE information, including correspondence with the Sponsor or local IRB/EC on file.
- The Sponsor will inform Investigators of any emerging safety issues as soon as possible, and at least prior to any planned dosing, following which the Investigator will subsequently inform participants.
- All studies that are conducted within any European country will comply with the [European Clinical Trial Directive 2005/28/EC](#), the [Clinical Trial Directive 2001/20/EC](#), and the [Detailed Guidance CT-3 \(2011/C 172/01\)](#) and Regulation 536/2014.

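### The SUSAR definition in Protocol 9.2.3 joins nature and severity with *and*, so a listed reaction in a worse than listed form can be classified as not a SUSAR

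*Protocol*

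**What the plan says.** Section 9.2.3 says that for an event to be a SUSAR "the AE must meet 3 criteria": it is serious, it is to some degree likely to be a reaction to the study drug, and it is unexpected. Unexpectedness is expressed as "the nature and severity of the reaction are not in agreement with the product information", followed by the gloss "i.e., the reaction is unexpected as per the reference safety information".

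The classification drives onward reporting. Section 9.6 states: "All SUSARs will be reported as required to the Competent Authorities of all involved participating countries". It leaves responsibilities, processes and timelines for expedited reporting to a Safety Management Plan, and it requires studies in Europe to follow the cited EU rules. Section 9.2.3 itself also sends SUSARs to ethics committees and IRBs.

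Reporting from site to sponsor does not depend on expectedness. Section 9.5 says: "For all AESI and SAEs, regardless of suspected causality, a completed AESI/SAE/Special Situation reporting form must be sent within 24 hours".

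**The concern.** A reaction can be unexpected because its type is new, or because a known type appears in a worse form. The definition should say plainly whether the second kind counts. As worded, it can be taken to say that it does not.

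This is relevant to an intravitreal product because the severe complication types of the injection are already known. Section 2.5 says that "potentially severe complications to IVT injections exist, including endophthalmitis, intraocular inflammation, cataract, retinal detachment, and vitreous hemorrhage". If complications of this kind are listed in the reference safety information (an assumption, since that document is not available here), a new signal could show itself as greater severity of a listed type. Two people applying Section 9.2.3 to the same case could then classify it differently. Investigators have a stake in this as well as the sponsor's safety staff, because Section 9.6 has them notify their local IRB or EC of SUSARs.

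**Working it through.** No arithmetic applies. The check takes one test case through the wording and then through the rest of the protocol.

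**Test case.** A serious event, suspected to be caused by study drug, of a type that is listed but more severe than listed. The first two criteria are met, so the third decides.

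**Possible readings of the third criterion.**

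- *Each must depart.* The sentence says of two things that they are not in agreement, which in ordinary usage means that neither agrees. Here nature agrees. The criterion fails and the event is not a SUSAR.
- *Taken together.* Nature and severity are treated as one description, which fails to match if any part of it does. Here severity does not match. The criterion is met and the event is a SUSAR.
- *The gloss governs.* The event is unexpected if the reference safety information makes it so. The answer then lies in a document that is not available here.

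The first is the most literal reading. The result changes with the reading chosen.

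**Does another section settle it?** No section restates the test with *or*. The protocol does use *or* elsewhere when any single change is meant to be enough:

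- in 9.2.1, for when a pre-existing condition becomes an AE;
- in 9.4.3 (c), for when a laboratory abnormality is recorded again;
- in 9.4.3 (e), for when a pre-existing condition is recorded as an AE.

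Those sections concern recording rather than expectedness, so they do not decide the matter. They do make it harder to treat the *and* in 9.2.3 as loose drafting for *or*.

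**What depends on the classification?**

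| Step | Section | Depends on SUSAR status? |
|---|---|---|
| SAE or AESI from site to sponsor within 24 hours | 9.5 | No |
| Immediate telephone report of a fatal or life-threatening event attributed to study drug | 9.5 | No |
| SAEs to IRB/EC, where applicable | 9.5 | No |
| Notice to central and local ECs/IRBs | 9.6 | Not solely; significant risks to subjects also trigger it |
| Emerging safety issues to investigators before any planned dosing | 9.6 | No |
| DMC safety review, including ad hoc review | 4.2.4.2, 9.1 | No |
| SUSAR report to Competent Authorities | 9.2.3, 9.6 | Yes |

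Only the last row rests on the SUSAR label alone. Section 12.3 also promises regulatory authorities safety updates under local requirements, so the event would not be hidden from them. The exposure is to the formal SUSAR report.

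**The case against.** The strongest reply is that the parenthesis controls. It states what the preceding words mean, so expectedness is whatever the reference safety information makes it, and the conjunction is only descriptive. The taken-together reading is also available on the text. The Safety Management Plan and the cited EU rules may already apply the right test.

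Part of this stands. A reader might infer that 9.2.3 definitely excludes worse than listed reactions. The documents do not go that far: the exclusion follows under one reading, and the section nowhere says that such reactions are expected. But the gloss does not close the gap. It names what to compare against and is silent on whether one departure is enough, and the only words in the documents that bear on that question are the ones in doubt.

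Three further inferences are tempting and should not be drawn.

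- *That such an event would have no expedited route, or that sites would be warned late while dosing continues.* Sections 9.5 and 9.6 contradict this, as the table shows.
- *That the gap can be sized by counting combinations of nature and severity.* A reaction of unlisted nature has no listed severity to agree with, so the combinations are not independent and such a count means nothing. The only arguable gap is listed nature with worse severity.
- *That the Safety Management Plan is wrong, or that the protocol conflicts with the EU rules.* The text of neither is among the documents, so neither can be asserted.

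**Conclusion.** The point holds as a minor wording correction to a stated rule. The most literal reading of the third SUSAR criterion omits a serious suspected reaction whose type is listed and whose severity exceeds what is listed, and nothing in the documents rules that reading out. The consequence is possible inconsistency or omission at the classification step; capture of the event and warnings to investigators are protected separately.

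No event count can be attached. That would need the reference safety information and the Safety Management Plan. The practical weight rests on two assumptions: that relevant ocular reactions are listed with a severity that can be exceeded, and that staff classify from the protocol wording.

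No planned output changes, because the SAP neither defines nor tabulates SUSARs. SAP Section 6 records that the sponsor stopped the study early, so the correction matters for any reporting still to be done, for the open-label extension planned in Protocol 4.2.1.3, and wherever this text is reused.

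**What to change.** In the third criterion of Section 9.2.3, replace *and* with *or* between nature and severity and make the verb singular, so that a departure in either one is enough. Keep the parenthesis, so that the reference safety information remains the comparator. Then check that the Safety Management Plan uses the same test, and align it only if it does not.

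The edit is one connective and its verb, plus that check. If the sponsor already applies the either-one test, practice does not change. If not, the downside is possibly a few more expedited reports.

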9.2.4 Adverse Events of Special Interest

9.3 Assessment of Adverse Events

The Investigator is responsible for assessing the severity and causality of AEs.

9.3.1 Assessment of Severity (Intensity) of Adverse Events

On the AE eCRF, the Investigator will use the adjectives MILD, MODERATE, or SEVERE to describe the maximum intensity of the AE. For purposes of consistency, these intensity grades are defined as follows:

- MILD: Awareness of sign, symptom, or event, but easily tolerated. Does not interfere with subject's usual function.
- MODERATE: Discomfort enough to cause interference to some extent with subject's usual function and may warrant intervention.
- SEVERE: Incapacitating and interferes significantly with subject's usual function and warrants intervention.

As described previously in Section 9.2.2, note the distinction between the severity and the seriousness of an AE. A severe event is not necessarily a serious event and may not meet the regulatory definition of serious. For example, a headache may be severe (interferes significantly with subject's usual function) but would not be classified as a serious AE unless it met one of the regulatory criteria for SAEs, listed above in Section 9.2.2.

Any change in severity should be noted in the eCRF, e.g., a change from mild to severe or a change from severe to moderate should be noted with the start and stop dates for each intensity.

9.3.2 Assessment of the Relationship of Adverse Events to Study Drug

The Investigator will make a causality assessment about the relationship of each AE to study drug. Assessment of causality is based on considering associative connections (time or place), pharmacological explanations, previous knowledge of the study drug, presence of characteristic clinical or pathological phenomena, underlying conditions in the study population, exclusion of other causes, and/or absence of alternative explanations. To ensure consistency of AE and SAE causality assessments, Investigators should apply the following general guideline:

Not Related: The AE has an etiology other than the study drug (e.g., preexisting medical condition, underlying disease, intercurrent illness, or concomitant medication); and/or the AE has no plausible temporal relationship to administration of the study drug (e.g., cancer diagnosed 2 days after dose of study drug).

Related: An AE that is related to the study drug or its administration (i.e., an event that follows a reasonable temporal sequence from administration of the study intervention, follows a known or

expected response pattern to the suspected intervention, that could not be reasonably explained by the known characteristics of the subject's clinical state).

For all AEs and SAEs, Investigators will make separate assessments of causality about the relationship of the event to study drug and to study procedures (i.e., IVT injection).

Note: The Investigator's assessment of causality for individual AE reports is part of the study documentation process and will be recorded in the subject's medical record, AE eCRF, and SAE form if applicable. Adverse events recorded without the Investigator's assessment of the relationship to study drug will be followed up until causality is assigned.

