9.4.1 Adverse Event Reporting Period

After signing of the Informed Consent all significant medical conditions including signs/symptoms of the underlying disease and known pre-existing medical conditions found during the screening period and up to initiation of dosing will be captured as medical history. Any event/condition, including those related to participation in the study or study procedures, those not related to underlying disease or pre-existing medical conditions already part of medical

history, and occurring before first dose of study treatment will be captured as a non-treatment emergent AE.

Any event/condition noted once the subject receives their dose of study drug will be captured as a treatment emergent AE. All AEs and SAEs regardless of attribution will be collected until at least 90 days following the last administration of study drug or the subject's EOS visit, whichever is later. At the last scheduled visit, the Investigator should instruct each subject to report to the Investigator any subsequent AEs/SAEs that the subject's personal physician believes could be related to prior study treatment.

SAEs unrelated to study treatment and non-serious AEs are to be followed until the last scheduled study visit (EOS visit), with the outcome at that point of time to be recorded in the eCRF. SAEs related to study treatment (Serious Adverse Drug Reactions) are to be followed until resolution or until they return to baseline, stabilize, or the subject is lost to follow-up. Resolution of AEs and SAEs (with dates) should be documented on the AE eCRF and SAE form (if applicable) and in the subject's medical record to facilitate source data verification. For some SAEs, the Sponsor or its designee may follow up by telephone, facsimile, electronic mail, and/or a monitoring visit to obtain additional case details deemed necessary to appropriately evaluate the SAE report (e.g., hospital discharge summary, consultant report, or autopsy report).

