10.9 Safety Analyses

10.9.1 Treatment Emergent Adverse Events

A treatment-emergent AE (TEAE) is defined as an event that was not present prior to administration of the first dose of study treatment and present after the first administration or if it represents the exacerbation of an event that was present prior to the first administration.

Adverse events noted during the study will be coded to system organ classes (SOCs) and preferred terms (PTs) using the Medical Dictionary for Regulatory Activities (MedDRA) dictionary. The overall incidence of TEAEs will be summarized by treatment group and classified by SOC and PT. Deaths, AE severity, serious AEs, relationship to study treatment and study discontinuation due to AE will also be tabulated by treatment group. An AE will be considered related to study treatment if the Investigator indicated the event is at least “possibly” related or if the relationship is missing. Adverse events with missing start dates, but with stop dates overlapping into the treatment period will be counted as treatment emergent. All AEs will be listed in subject listings and summarized by numbers and percentages of subjects by treatment group.

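### Read literally, Protocol 9.3.2 sets a narrower test for a related adverse event than 9.2.3, 9.5 and 10.9.1 use, and its two-level scale has no *possibly* level

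*Protocol*

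**What the plan says.** Protocol 9.3.2 offers two categories. *Related* covers the drug or its administration. Its explanation sets the timing condition first and leads straight into the pattern condition: "i.e., an event that follows a reasonable temporal sequence from administration of the study intervention, follows a known or". The rest of the pattern condition, and the third condition, read "expected response pattern to the suspected intervention, that could not be reasonably explained by the known characteristics of the"; what must fail to explain the event is the clinical state of the person treated. *Not Related* applies where "The AE has an etiology other than the study drug (e.g., preexisting medical condition, underlying disease, intercurrent illness, or concomitant medication"), and/or where the timing is implausible. The two definitions are introduced with the words "Investigators should apply the following general guideline".

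Four other sections depend on the causality answer or set a causality threshold:

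- Protocol 9.2.3: for a SUSAR it is enough that "there is a certain degree of probability that the event is a reaction to the study drug being researched", together with seriousness and unexpectedness against the reference safety information.
- Protocol 9.4.1: "SAEs related to study treatment (Serious Adverse Drug Reactions) are to be followed until resolution" (or return to baseline, stabilisation or loss to follow-up). Unrelated serious events are followed only to the end-of-study visit.
- Protocol 9.5: serious events arising after participation and "considered by the Investigator to be possibly related to study drug must also be reported".
- Protocol 10.9.1: the counting rule begins "An AE will be considered related to study treatment if the Investigator indicated the event is at least"; the level it then names is *possibly*, and events with no recorded relationship are added to the count.

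**The concern.** The section that collects the causality answer uses a stricter test than sections that use it. Nothing in the definition of *Related* separates its three conditions with an *or*, so the literal reading requires all of them. A reaction not seen before struggles with the second condition. An event that the disease could also produce struggles with the third.

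Both kinds of event matter in this trial. Protocol 2.3 describes RP as progressive vision loss, and lists changes in BCVA and macular edema among the potential adverse events to be detected early. Exclusion criterion 4 in Protocol 5.3.2 admits subjects whose cystoid macular edema has been stable for 3 months. For such subjects, disease and treatment can be competing explanations of the same finding.

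At stake are which serious reactions qualify as SUSARs, how long some serious events are followed, and how many events are counted as related.

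**Working it through.** No arithmetic applies: the plan states no figure here. The check sets the sections side by side and then runs typical events through them.

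**Thresholds**

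| Protocol section | Use of causality | Threshold |
|---|---|---|
| 9.3.2 | Investigator's answer | Timing **and** recognised or anticipated pattern **and** not reasonably explained by clinical state |
| 9.2.3 | SUSAR qualification | Some probability of a drug reaction |
| 9.4.1 | Length of follow-up of serious events | Related or unrelated to study treatment |
| 9.5 | Reporting of serious events after participation | Possibly related |
| 10.9.1 | Count of related events | Possibly related or higher, or relationship missing |

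The entries for 9.2.3, 9.5 and 10.9.1 are all wider than the 9.3.2 test. The last two name a level that 9.3.2 does not offer.

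**Events run through 9.3.2**

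1. *Well timed, new pattern, no disease explanation.* It fails the pattern condition, so it is not *Related*. It has plausible timing and no other identified cause, so it is not *Not Related* either. It falls in the gap between the two. Under 9.2.3 the same event, if serious, could be a SUSAR.
2. *Well timed, recognised pattern, disease also plausible.* Examples are vision loss, or macular edema in a subject admitted with stable cystoid macular edema. If clinical state reasonably explains it, the third condition fails. *Not Related* lists pre-existing conditions and underlying disease as example causes, which pulls the event there. Under 10.9.1 it is the sort of event that a threshold of possibly related should catch.
3. *Well timed, recognised pattern, more severe than the reference safety information lists.* It can be *Related* and also unexpected, so a SUSAR remains possible.
4. *Vision loss faster or more severe than RP reasonably explains.* It can meet all three conditions and be *Related*.

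Cases 1 and 2 show the mismatch. Cases 3 and 4 show that it is not an absolute bar.

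**Does the missing-value rule rescue cases 1 and 2?** Largely not. Section 10.9.1 counts a missing relationship as related, but 9.3.2 has missing causality chased until it is assigned. An ambiguous event is therefore likely to end in one of the two categories, not remain missing.

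**What does not depend on the answer?** Section 9.5 requires every serious event and every event of special interest to be notified within 24 hours, whatever the suspected cause. Only the additional telephone call for fatal or life-threatening events turns on the investigator's attribution. Section 10.9.1 tabulates all treatment-emergent events by treatment group, and these tables do not use the relationship.

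**What reaches the close-out report?** SAP section 6 limits the adverse-event tables to an overview. SAP 5.6 names no table of related events. The output shells are in a separate document, so whether the overview has a row for related events cannot be seen.

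**The case against.** A reader might infer that unexpected reactions and RP-type events can never be *Related*. The documents do not support that. The definitions are a general guideline, and the sentence before them lists causality factors joined by *and/or*, so another possible cause is one factor to weigh. A recognised response pattern is also a different test from expectedness, which 9.2.3 judges by nature and severity against the reference safety information. The third condition asks whether clinical state *reasonably* explains the event. Cases 3 and 4 above follow from these points. What remains is that investigators are told to apply the guideline for consistency, and the *and/or* list does not change the wording of the two categories.

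A reader might also infer that the whole safety profile is biased in the drug's favour. That does not follow. Protocol 10.1 says all adverse events count toward the safety profile, an excess in one arm would appear in the tables of all treatment-emergent events, and clinical assessments are made by masked physicians. The loss is confined to what depends on the causality answer.

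Three further points narrow the concern. First, on a two-level scale *possibly or higher* can be mapped to *Related*, so the 10.9.1 count can be computed. This stands, but the result is then a count on the narrow test, not the inclusive one that 10.9.1 describes. Second, 9.2.3 does not refer to 9.3.2, and 9.6 leaves expedited reporting to a Safety Management Plan that is not available here; that plan may apply a wider test. Third, 9.4.1 follows even unrelated serious events to the end-of-study visit, so the loss of follow-up touches only those still open then.

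**Conclusion.** The concern holds as an inconsistency of thresholds. Followed literally, 9.3.2 is narrower than 9.2.3, 9.5 and 10.9.1, and it leaves a gap between its own two categories. It steers new-pattern reactions, and ocular events that the disease or a permitted baseline condition could explain, away from *Related*. The possible effects are too few events qualifying as SUSARs, too low a count of related events, and follow-up that stops at the end-of-study visit for some open serious events.

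The size cannot be calculated, because the documents give no event rates and no causality data; only the direction is clear. For the close-out tables the effect is limited or unknown.

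The conclusion rests on two assumptions: that investigators apply the 9.3.2 wording as written, and that the investigator's answer feeds SUSAR qualification without a wider sponsor test in the Safety Management Plan. If either fails, the practical effect is smaller, but the sections still need to be reconciled because they use different scales.

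**What to change.** Put Protocol 9.2.3, 9.3.2, 9.4.1, 9.5 and 10.9.1 on one causality scale:

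- In 9.3.2, define *Related* as a reasonable possibility that the drug or its administration caused or contributed to the event, whether or not the pattern is already known and even if another cause is also plausible.
- Define *Not Related* as its complement: implausible timing, or another cause that leaves no reasonable possibility of a contribution. This closes the gap.
- In 9.5 and 10.9.1, replace the possibly-related wording with the *Related* level so defined, and have 9.2.3 and 9.4.1 refer to the same level.

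If the database is not yet locked, re-query causality for ocular adverse events and for serious adverse events under the new wording. If it is locked, state in the abbreviated clinical study report that relationship was collected on the narrower test and that related-event counts may be low.

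The cost is protocol and eCRF-guideline wording and, before lock, one query round. The downside is that more events will be classed as related, including some that the disease caused.
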